### **10.3. Quality Control (Study Monitoring)**

- In accordance with applicable regulations including GCP, and GSK procedures, GSK monitors will contact the site prior to the start of the study to review with the site staff the protocol, study requirements, and their responsibilities to satisfy regulatory, ethical, and GSK requirements.
- When reviewing data collection procedures, the discussion will also include identification, agreement and documentation of data items for which the CRF will serve as the source document.

GSK will monitor the study and site activity to verify that the:

- Data are authentic, accurate, and complete.
- Safety and rights of subjects are being protected.
- Study is conducted in accordance with the currently approved protocol and any other study agreements, GCP, and all applicable regulatory requirements.

The investigator and the head of the medical institution (where applicable) agrees to allow the monitor direct access to all relevant documents

### **10.4. Quality Assurance**

- To ensure compliance with GCP and all applicable regulatory requirements, GSK may conduct a quality assurance assessment and/or audit of the site records, and the regulatory agencies may conduct a regulatory inspection at any time during or after completion of the study.
- In the event of an assessment, audit or inspection, the investigator (and institution) must agree to grant the advisor(s), auditor(s) and inspector(s) direct access to all relevant documents and to allocate their time and the time of their staff to discuss the conduct of the study, any findings/relevant issues and to implement any corrective and/or preventative actions to address any findings/issues identified.

### **10.5. Study and Site Closure**

- Upon completion or premature discontinuation of the study, the GSK monitor will conduct site closure activities with the investigator or site staff, as appropriate, in accordance with applicable regulations including GCP, and GSK Standard Operating Procedures.
- GSK reserves the right to temporarily suspend or prematurely discontinue this study at any time for reasons including, but not limited to, safety or ethical issues or severe non-compliance. For multicenter studies, this can occur at one or more or at all sites.
- If GSK determines such action is needed, GSK will discuss the reasons for taking such action with the investigator or the head of the medical institution (where applicable). When feasible, GSK will provide advance notification to the

investigator or the head of the medical institution, where applicable, of the impending action.

- If the study is suspended or prematurely discontinued for safety reasons, GSK will promptly inform all investigators, heads of the medical institutions (where applicable) and/or institution(s) conducting the study. GSK will also promptly inform the relevant regulatory authorities of the suspension or premature discontinuation of the study and the reason(s) for the action.
- If required by applicable regulations, the investigator or the head of the medical institution (where applicable) must inform the IRB/IEC promptly and provide the reason for the suspension or premature discontinuation.

## **10.6. Records Retention**

- Following closure of the study, the investigator or the head of the medical institution (where applicable) must maintain all site study records (except for those required by local regulations to be maintained elsewhere), in a safe and secure location.
- The records must be maintained to allow easy and timely retrieval, when needed (e.g., for a GSK audit or regulatory inspection) and must be available for review in conjunction with assessment of the facility, supporting systems, and relevant site staff.
- Where permitted by local laws/regulations or institutional policy, some or all of these records can be maintained in a format other than hard copy (e.g., microfiche, scanned, electronic); however, caution needs to be exercised before such action is taken.
- The investigator must ensure that all reproductions are legible and are a true and accurate copy of the original and meet accessibility and retrieval standards, including re-generating a hard copy, if required. Furthermore, the investigator must ensure there is an acceptable back-up of these reproductions and that an acceptable quality control process exists for making these reproductions.
- GSK will inform the investigator of the time period for retaining these records to comply with all applicable regulatory requirements. The minimum retention time will meet the strictest standard applicable to that site for the study, as dictated by any institutional requirements or local laws or regulations, GSK standards/procedures, and/or institutional requirements.
- The investigator must notify GSK of any changes in the archival arrangements, including, but not limited to, archival at an off-site facility or transfer of ownership of the records in the event the investigator is no longer associated with the site.

## **10.7. Provision of Study Results to Investigators, Posting of Information on Publicly Available Clinical Trials Registers and Publication**

Where required by applicable regulatory requirements, an investigator signatory will be identified for the approval of the clinical study report. The investigator will be provided reasonable access to statistical tables, figures, and relevant reports and will have the opportunity to review the complete study results at a GSK site or other mutually-agreeable location.

GSK will also provide the investigator with the full summary of the study results. The investigator is encouraged to share the summary results with the study subjects, as appropriate.

GSK will provide the investigator with the randomization codes for their site only after completion of the full statistical analysis.

The procedures and timing for public disclosure of the results summary and for development of a manuscript for publication will be in accordance with GSK Policy.

A manuscript will be progressed for publication in the scientific literature if the results provide important scientific or medical knowledge.

## **10.8. Safety Review Team (SRT)**

Instream review of unblinded safety data including AE, SAEs, vital signs and laboratory data will be conducted by a SRT during the study conduct. The membership of the SRT (including members of the central GSK study team) and the proposed frequency of review will be documented in the SRT charter.

## 12. APPENDICES

### 12.1. Appendix 1 – Abbreviations and Trademarks

#### Abbreviations

AE	Adverse Event
BMI	Body Mass Index
BCR	B-cell receptor
CCLE	Chronic Cutaneous Lupus Erythematosus
CLE	Cutaneous Lupus Erythematosus
CONSORT	Consolidated Standards of Reporting Trials
CRF	Case Report Form
CV	Cardio Vascular
EFD	Embryofoetal development
Fc $\epsilon$ R1	Fc epsilon receptors
FRP	Females of Reproductive Potential
FSH	Follicle Stimulating Hormone
FTIH	First Time in Human
GCP	Good Clinical Practice
GCSP	Global Clinical Safety and Pharmacovigilance
GSK	GlaxoSmithKline
HIV	Human Immuno-Deficiency Virus
HRT	Hormone Replacement Therapy
IDSL	Integrated Data Standards Library
IEC	Independent Ethics Committee
IFN	Interferon
IRB	Institutional Review Board
LET	Lupus Erythematosus Tumidus
MALDI-MS	Matrix Assisted Laser Desorption Ionization-Imaging Mass Spectrometry
mRNA	Messenger-Ribonucleic Acid
MSDS	Material Safety Data Sheet
NOAEL	No Observed Adverse Effect Level
PD	Pre-dose
PK	Pharmacokinetics
pSYK	Phosporylated- Spleen Tyrosine Kinase
PV	Photoprovocation
QTcB	QT interval corrected for heart rate according to Bazett's formula
QTcF	QT interval corrected for heart rate according to Fridericia's formula
QoL	Quality of Life
RAP	Reporting and Analysis Plan
SAE	Serious Adverse Event
SCLE	Sub-acute Cutaneous Lupus Erythematosus

SD	Standard Deviation
SLE	Systemic Lupus Erythematosus
SRM	Study Reference Manual
SRT	Safety Review Team
SYK	Spleen Tyrosine Kinase

**Trademark Information**

Trademarks of the GlaxoSmithKline group of companies	Trademarks not owned by the GlaxoSmithKline group of companies
NONE	None

## 12.2. Appendix 2: Liver Safety – Study Treatment Restart

### Phase II liver chemistry stopping criteria and required follow up assessments

Liver Chemistry Stopping Criteria – Liver Stopping Event	
ALT-absolute	ALT $\geq$ 5xULN
ALT Increase	ALT $\geq$ 3xULN persists for $\geq$ 4 weeks
Bilirubin	ALT $\geq$ 3xULN and bilirubin $\geq$ 2xULN (>35% direct bilirubin)
INR^2	ALT $\geq$ 3xULN and INR>1.5, if INR measured
Cannot Monitor	ALT $\geq$ 3xULN and cannot be monitored weekly for 4 weeks
Symptomatic	ALT $\geq$ 3xULN associated with symptoms (new or worsening) believed to be related to liver injury or hypersensitivity
Required Actions and Follow up Assessments following ANY Liver Stopping Event	
Actions	

 
• Immediately discontinue study treatment
 
• Report the event to GSK within 24 hours
 
• Complete the liver event CRF and complete an SAE data collection tool if the event also meets the criteria for an SAE
 
• Perform liver event follow up assessments
 
• Monitor the subject until liver chemistries resolve, stabilize, or return to within baseline (see MONITORING below)
 
• Do not restart/rechallenge subject with study treatment unless allowed per protocol and GSK Medical Governance approval is granted
 
• If restart/rechallenge not allowed per protocol or not granted, permanently discontinue study treatment and may continue subject in the study for any protocol specified follow up assessments
 
 
MONITORING:
 
For bilirubin or INR criteria:
	
 
• Viral hepatitis serology
 
• Blood sample for pharmacokinetic (PK) analysis, obtained within 24 hours after last dose
 
• Serum creatine phosphokinase (CPK) and lactate dehydrogenase (LDH).
 
• Fractionate bilirubin, if total bilirubin <math>\geq</math> 2xULN
 
• Obtain complete blood count with differential to assess eosinophilia
 
• Record the appearance or worsening of clinical symptoms of liver injury, or hypersensitivity, on the AE report form
 
• Record use of concomitant medications on the concomitant medications report form including acetaminophen, herbal remedies, other over the counter medications.
 
• Record alcohol use on the liver event alcohol intake case report form
 


 
Repeat liver chemistries (include ALT, AST, alkaline phosphatase, bilirubin) and perform liver event follow up assessments within 24 hrs
 
Monitor subjects twice weekly until liver chemistries resolve, stabilize or return to within baseline
 
A specialist or hepatology consultation is recommended
 
 
For All other criteria:
 
 
Repeat liver chemistries (include ALT, AST, alkaline phosphatase, bilirubin) and perform liver event follow up assessments within 24-72 hrs
 
Monitor subjects weekly until liver chemistries resolve, stabilize or return to within baseline
 
	
For bilirubin or INR criteria:
 
 
Anti-nuclear antibody, anti-smooth muscle antibody, Type 1 anti-liver kidney microsomal antibodies, and quantitative total immunoglobulin G (IgG or gamma globulins).
 
Serum acetaminophen adduct HPLC assay (quantifies potential acetaminophen contribution to liver injury in subjects with definite or likely acetaminophen use in the preceding week [James, 2009]).
 
Liver imaging (ultrasound, magnetic resonance, or computerised tomography) and /or liver biopsy to evaluate liver disease: complete Liver Imaging and/or Liver Biopsy CRF forms.
 

--	--

1. Serum bilirubin fractionation should be performed if testing is available. If serum bilirubin fractionation is not immediately available, discontinue study treatment for that subject if **ALT  $\geq$  3xULN and bilirubin  $\geq$  2xULN**. Additionally, if serum bilirubin fractionation testing is unavailable, **record presence of detectable urinary bilirubin on dipstick**, indicating direct bilirubin elevations and suggesting liver injury.
2. All events of **ALT  $\geq$  3xULN and bilirubin  $\geq$  2xULN** ( $>35\%$  direct bilirubin) or **ALT  $\geq$  3xULN and INR  $>1.5$** , if INR measured which may indicate severe liver injury (possible 'Hy's Law'), **must be reported as an SAE (excluding studies of hepatic impairment or cirrhosis)**; INR measurement is not required and the threshold value stated will not apply to subjects receiving anticoagulants
3. New or worsening symptoms believed to be related to liver injury (such as fatigue, nausea, vomiting, right upper quadrant pain or tenderness, or jaundice) or believed to be related to hypersensitivity (such as fever, rash or eosinophilia)
4. Includes: Hepatitis A IgM antibody; Hepatitis B surface antigen and Hepatitis B Core Antibody (IgM); Hepatitis C RNA; Cytomegalovirus IgM antibody; Epstein-Barr viral capsid antigen IgM antibody (or if unavailable, obtain heterophile antibody or monospot testing); Hepatitis E IgM antibody
5. PK sample may not be required for subjects known to be receiving placebo or non-GSK comparator treatments.) Record the date/time of the PK blood sample draw and the date/time of the last dose of study treatment prior to blood sample draw on the CRF. If the date or time of the last dose is unclear, provide the subject's best approximation. If the date/time of the last dose cannot be approximated OR a PK sample cannot be collected in the time period indicated above, do not obtain a PK sample. Instructions for sample handling and shipping are in the SRM.

Phase II liver chemistry increased monitoring criteria with continued therapy	
ALT 3xULN and <5xULN and bilirubin <2xULN, without symptoms believed to be related to liver injury or hypersensitivity, and who can be monitored weekly for 4 weeks	

• Notify the GSK medical monitor within 24 hours of learning of the abnormality to discuss subject safety.

• Subject can continue study treatment

• Subject must return weekly for repeat liver chemistries (ALT, AST, alkaline phosphatase, bilirubin) until they resolve, stabilise or return to within baseline

• If at any time subject meets the liver chemistry stopping criteria, proceed as described above

• If, after 4 weeks of monitoring, ALT <3xULN and bilirubin <2xULN, monitor subjects twice monthly until liver chemistries normalize or return to within baseline.

## 12.3. Appendix 3: Definition of and Procedures for Recording, Evaluating, Follow-Up and Reporting of Adverse Events

### 12.3.1. Definition of Adverse Events

#### Adverse Event Definition:

- An AE is any untoward medical occurrence in a patient or clinical investigation subject, temporally associated with the use of a medicinal product, whether or not considered related to the medicinal product.
- NOTE: An AE can therefore be any unfavorable and unintended sign (including an abnormal laboratory finding), symptom, or disease (new or exacerbated) temporally associated with the use of a medicinal product.

#### Events meeting AE definition include:

- Any abnormal laboratory test results (hematology, clinical chemistry, or urinalysis) or other safety assessments (e.g., ECGs, radiological scans, vital signs measurements), including those that worsen from baseline, and felt to be clinically significant in the medical and scientific judgement of the investigator.
- Exacerbation of a chronic or intermittent pre-existing condition including either an increase in frequency and/or intensity of the condition.
- New conditions detected or diagnosed after study treatment administration even though it may have been present prior to the start of the study.
- Signs, symptoms, or the clinical sequelae of a suspected interaction.
- Signs, symptoms, or the clinical sequelae of a suspected overdose of either study treatment or a concomitant medication (overdose per se will not be reported as an AE/SAE unless this is an intentional overdose taken with possible suicidal/self-harming intent. This should be reported regardless of sequelae).
- "Lack of efficacy" or "failure of expected pharmacological action" per se will not be reported as an AE or SAE. However, the signs and symptoms and/or clinical sequelae resulting from lack of efficacy will be reported if they fulfil the definition of an AE or SAE.
- The signs and symptoms and/or clinical sequelae resulting from lack of efficacy will be reported if they fulfil the definition of an AE or SAE. Also, "lack of efficacy" or "failure of expected pharmacological action" also constitutes an AE or SAE.

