### 3. OBJECTIVE(S) AND ENDPOINT(S)

Objectives	Endpoints
Primary	

 
To evaluate the safety and tolerability of repeat doses of a cream formulation of GSK 2646264 in patients with CLE
 
	
 
Safety and tolerability by laboratory tests, vital signs, 12-lead ECG, and AE reporting.
 

Secondary	

 
To determine the effect of GSK2646264 on the reduction in clinical activity score from baseline in treated PV and existing CLE lesions
 
To evaluate the plasma concentrations of GSK2646264 in patients with CLE
 
To determine the effect of GSK2646264 on expression of IFN mRNA signature in skin biopsies in treated PV and existing CLE lesions
 
	
 
Change from baseline of components of a modified RCLASI- composite clinical activity score at day 14 and day 28 in PV and existing lesions in erythema, oedema, dyspigmentation and (scaling in existing CLE lesions only)
 
PK parameters will be summarised
 
Change from baseline in IFN mRNA signature in skin biopsies at day 28 in PV and existing CLE lesions
 

Exploratory	

 
To determine the effect of GSK2646264 on expression of IFN protein markers in skin biopsies in treated PV and existing CLE lesions
 
To determine the effect of GSK2646264 on expression of pSYK and SYK protein in skin biopsies in treated PV and existing CLE lesions
 
To determine the effect of
 
	
 
Change from baseline in IFN proteins (eg MxA, CXCL10) in skin biopsies at day 28 in PV and existing CLE lesions
 
Change from baseline in pSYK and SYK protein in skin biopsies at day 28 in PV and existing CLE lesions
 
Change from baseline in immune cell
 

Objectives	Endpoints

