### **9.2. Sample Size Considerations**

There are no formal calculations of power or sample size for this study. The sample sizes have been chosen based on feasibility, to primarily allow the assessment of safety and tolerability of GSK2646264 in patients with CLE.

[figure not shown]
We will recruit approximately 25 patients with CLE into the study with the aim to randomise approximately 20 patients. Approximately 10 patients will undergo PV in group A. PV response rates are estimated at 50% and we expect up to 5 PV positive patients to be randomised into the study. We aim to randomise approximately 15 patients into group B of the study. All patients will be treated with both GSK2646264 and placebo on separate lesions (see Section 6.1 for details).

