#### Events NOT meeting definition of an AE include:

- Any clinically significant abnormal laboratory findings or other abnormal safety assessments which are associated with the underlying disease, unless judged by the

investigator to be more severe than expected for the subject's condition.

- The disease/disorder being studied or expected progression, signs, or symptoms of the disease/disorder being studied, unless more severe than expected for the subject's condition.
- Medical or surgical procedure (e.g., endoscopy, appendectomy): the condition that leads to the procedure is an AE.
- Situations where an untoward medical occurrence did not occur (social and/or convenience admission to a hospital).
- Anticipated day-to-day fluctuations of pre-existing disease(s) or condition(s) present or detected at the start of the study that do not worsen.

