11.8.5. Safety Tables

Safety : Tables					
No.	Population	IDSL / TST ID / Example Shell	Title	Programming Notes	Deliverable [Priority]
Adverse Events					
2.1.	Safety	CP_AE1p	Summary of All Adverse Events by System Organ Class (Group B-Natural Lesions)	Only Total adverse events will be summarised.	SAC
2.2.	Safety	CP_AE1p	Summary All Drug-Related Adverse Events by System Organ Class (Group B-Natural Lesions)	Only Total adverse events will be summarised.	SAC

Safety : Tables					
No.	Population	IDSL / TST ID / Example Shell	Title	Programming Notes	Deliverable [Priority]
Serious and Other Significant Adverse Events					
2.3.	Safety	CP_AE1p	Summary of Serious Adverse Events by System Organ Class (Group B-Natural Lesions)	Only Total adverse events will be summarised.	SAC
2.4.	Safety	CP_AE1p	Summary of Adverse Events Leading to Withdrawal from Study / Permanent Discontinuation of Study Treatment by Overall Frequency (Group B-Natural Lesions)	Only Total adverse events will be summarised.	SAC
Laboratory: Chemistry					
2.5.	Safety	LB1	Summary of Chemistry Changes from Baseline (Group B-Natural Lesions)	Treatment column will not be displayed.	SAC
2.6.	Safety	LB3	Summary of Emergent Chemistry Results Relative to Normal Range (Group B-Natural Lesions)	Treatment columns will be replaced by one 'Part B' column	SAC
Laboratory: Hematology					
2.7.	Safety	LB1	Summary of Hematology Changes from Baseline (Group B-Natural Lesions)	Includes baseline values. Treatment column will not be displayed.	SAC
2.8.	Safety	LB3	Summary of Emergent Hematology Results Relative to Normal Range (Group B-Natural Lesions)	As notes for Chemistry T2.12.	SAC
Laboratory: Urinalysis					
2.9.	Safety	LB1	Summary of Urine Concentration Changes from Baseline (Group B-Natural Lesions)	Includes Baseline values. Treatment column will not be displayed.	SAC
2.10.	Safety	LB2	Summary of Emergent Urinalysis Dipstick Results (Group B-Natural Lesions)	As above for Chemistry, using dipstick categories.	SAC
Laboratory: Hepatobiliary (Liver)					
2.11.	Safety	LIVER1	Summary of Liver Monitoring/Stopping Event Reporting (Group B-Natural Lesions)	Treatment columns will be replaced by one 'Part B' column	SAC

Safety : Tables					
No.	Population	IDSL / TST ID / Example Shell	Title	Programming Notes	Deliverable [Priority]
2.12.	Safety	LIVER10	Summary of Subjects Meeting Emergent Hepatobiliary Laboratory Abnormality Criteria (Group B-Natural Lesions)	Treatment columns will be replaced by one 'Part B' column	SAC

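### Protocol 12.3.1 says both that lack of efficacy in itself is not an adverse event and that it is one, so the descriptive AE count could vary with the bullet a site follows

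*Protocol*

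**What the plan says.** Protocol 12.3.1 lists events that meet the AE definition. Its last two bullets both deal with lack of efficacy and failure of the expected drug action.

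- The first says that this "per se will not be reported as an AE or SAE", and that resulting signs, symptoms or sequelae are reported if they meet the AE or SAE definition.
- The second repeats the rule on signs, symptoms and sequelae, then adds that lack of efficacy "also constitutes an AE or SAE".

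The next list in the same section gives events that do not meet the definition. It includes "The disease/disorder being studied or expected progression, signs, or symptoms of the disease/disorder being studied", unless more severe than expected for that subject.

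The primary endpoint (Protocol 3) is "Safety and tolerability by laboratory tests, vital signs, 12-lead ECG, and AE reporting". On treatment, Protocol 9.2 says: "All patients will be treated with both GSK2646264 and placebo on separate lesions". SAP 11.2.1 explains that safety displays are not split by treatment because each subject receives both creams at once. The programming note for AE Tables 2.1 to 2.4 (SAP 11.8.5) reads "Only Total adverse events will be summarised".

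**The concern.** Both bullets are in the current protocol body, and neither is marked as superseded. They agree on everything except lack of efficacy itself, and there they are opposites. An investigator who sees an unimproved lesion and nothing else has one bullet saying not to report it and one saying that it is an AE or SAE.

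The situation is foreseeable. Each treated subject has a placebo-treated lesion for 28 days, and site staff are blinded to which lesion that is. A report of an unimproved lesion would enter the AE totals, which do not show which lesion or cream gave rise to it. The AE rate could then differ between investigators or centres for reasons unrelated to safety. The documents foresee more than one centre: Amendment 3 applies to all sites, and SAP Table 1.4 counts subjects by country and centre.

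The definition also controls SAEs. Protocol 12.3.2 says that an event which is not an AE cannot be an SAE, and both conflicting bullets name SAEs.

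**Working it through.** **1. The rules side by side**

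| Situation | First bullet | Second bullet | List of events not meeting the definition |
|---|---|---|---|
| Signs, symptoms or sequelae that meet the AE definition | Report | Report | Report if more severe than expected |
| Lack of efficacy in itself | Do not report | AE or SAE | Expected disease signs are not AEs |

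The conflict is confined to the second row. There the second bullet stands alone against the first bullet and the exclusion list. The exclusion list does not cancel it, because the second bullet is not made subject to that list.

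**2. Which outputs are exposed**

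- Table 2.1 (all AEs): any such report is counted.
- Table 2.2 (drug-related AEs): counted only if judged related.
- Table 2.3 (serious AEs): counted only if judged serious.
- Table 2.4 (AEs leading to withdrawal or discontinuation): counted only if the report led to either.
- Laboratory, vital-sign and ECG tables: not affected.
- Local tolerability tables: not affected. They use their own scale and are shown by treatment.

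SAP 2.1 states that nobody was randomised in Group A, so only Group B matters.

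**3. The plan's own interval, reproduced**

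Protocol 9.2.1 uses a flat Beta(1,1) prior, so x events in n subjects give a Beta(1 + x, 1 + n − x) posterior. For x = 1 and n = 15 this is Beta(2, 15), with 2.5% and 97.5% points 0.016 and 0.302. The protocol states 0.02 to 0.30, which agrees.

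**4. Illustration by the same method**

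Start from the protocol's example of 1 subject with an event in 15. Let k further subjects have lack of efficacy as their only reported event. The documents give no value for k, so the table shows its range as an assumption. The count is (1 + k)/15 and the posterior is Beta(2 + k, 15 − k).

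| k (assumed) | Count | Rate | 95% interval |
|---|---|---|---|
| 0 (first bullet followed) | 1/15 | 7% | 2 to 30% |
| 1 | 2/15 | 13% | 4 to 38% |
| 3 | 4/15 | 27% | 11 to 52% |
| 5 | 6/15 | 40% | 20 to 65% |
| 8 | 9/15 | 60% | 35 to 80% |
| 14 | 15/15 | 100% | 79 to 100% |

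A subject who already has another AE would add to the number of events but not to the number of subjects with any AE.

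**5. The outer bound for this event type alone**

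The count is 0/15 if every site follows the first bullet and at most 15/15 if every site follows the second and reports every subject. The Clopper-Pearson limits are:

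- 0/15: upper limit 1 − 0.025^(1/15) = 21.8%, so 0 to 21.8%.
- 15/15: lower limit 0.025^(1/15) = 78.2%, so 78.2 to 100%.

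This shows only that the proportion could lie anywhere from 0 to 1. It is not a forecast.

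**The case against.** The strongest reply accepts the contradiction and disputes that it matters.

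- **The rest of the section points one way.** The general definition requires something untoward, and disease counts when new or worsened. The exclusion list removes the disease under study and ordinary fluctuation of existing conditions that do not worsen. An unchanged baseline lesion fits those exclusions, so most investigators would probably not report it. This stands and lowers the likely size. It does not remove the sentence that says the opposite.
- **AEs are found by open questions** (Protocol 7.4.1.2), and non-response has its own record in the clinical score on Days 1, 14 and 28 (Protocol 7.1.3). This also stands as a reason to expect few such reports.
- **Such reports can be found afterwards.** SAP Listing 14 shows all AEs, and Listing 17 links coded terms to verbatim text. This stands, and it makes the remedy cheap. However, no planned table sets the reports apart.
- **Placebo has no expected drug action that could fail.** This helps little, because blinded staff cannot tell which lesion received placebo.
- **No test is affected.** Protocol 9.1 plans no formal comparison for safety, so neither type I error nor power is involved. This stands in full.

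A reader might infer that nearly every subject would generate such a report, since every subject has a placebo lesion. The documents do not support that. They give no non-response rate on either cream, and a persisting lesion is not the same as a reported lack of efficacy.

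**Conclusion.** The point holds as an internal contradiction in a definition that feeds the primary endpoint. Because AEs are summarised only as totals, the descriptive AE count, chiefly in Table 2.1, could vary with the bullet a site follows.

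The size is unknown. Three extra subjects would move the protocol's 1/15 example from 7% to 27%, but three is an assumed number. The range 0/15 to 15/15 is a theoretical bound. It also uses the planned 15 subjects; the SAP cites the small number of patients without giving the number randomised in Group B.

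Two stronger readings are tempting. One is that the primary safety result is unreliable as a whole; it is not, because the other named components do not use this definition. The other is that sites did report differently; neither document contains evidence of that. The text is wrong as written and should be corrected, but the consequence is limited.

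**What to change.** 1. In Protocol 12.3.1, delete the statement that lack of efficacy or failure of expected drug action is itself an AE or SAE. Keep the bullet that excludes it, which agrees with the exclusion of expected disease signs in the same section. The rule on resulting signs, symptoms and sequelae is unchanged, because the retained bullet already states it.
2. For data already collected, which a protocol deletion cannot change, add a rule to the SAP: flag in the AE listings any AE recorded solely as lack of efficacy, and show Tables 2.1 to 2.4 with and without such reports. If there are none, one sentence in the study report is enough.

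The cost is a minor protocol amendment, with ethics review as applicable under Protocol 10.2, one flag in the AE dataset and a small amount of extra tabulation. No visits, assessments or subjects are added.
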